5.15 Heart Rhythm Monitoring

Holter Monitors, ECG, and Trans telephonic monitors (TTM) will be used to monitor the subjects' heart rhythm post-treatment.

Holter Monitor:

- 24-hour Holter monitors are required at the baseline, 6, 12 and 15-month visits.

As part of the 6- and 12 and 15-month follow up visit assessment, all subjects will undergo 24-hour Holter Monitoring to assess their heart rhythm. Holter Monitor data will be sent to the Core Laboratory for independent interrogation and analysis.

Trans telephonic Monitors (TTM):

Trans telephonic monitors (TTM) will be provided to each subject at the 6-month follow-up visit for scheduled transmissions of heart rhythm status. Subjects will be instructed to transmit all emergent symptomatic cardiac events and follow a detailed schedule if the subject remains asymptomatic post ablation during the Evaluation Period (Day 181-450).

The TTM transmission schedule:

- Each subject will be provided with a TTM device at the 6-month visit.

- Subjects will complete a test transmission upon receipt of the TTM device to demonstrate a working understanding of the device.
- Transmission will be performed monthly during the Evaluation Period, starting at day 181 (i.e. at months 7, 8, 9, 10, 11, 12, 13, 14, 15) post index AF ablation procedure. Monthly TTM transmissions are sent directly to the Core Lab.
- All symptomatic cardiac episodes should be recorded and transmitted soon after the event occurs.

5.16 Neurological Assessment (NIHSS)

The NIH Stroke Scale (NIHSS) assessment will be used for neurologic evaluation pre and post ablation procedures. The NIHSS will be administered by a certified person at baseline and hospital discharge, or 24 hours after the procedure, whichever is later. The NIHSS results will be recorded in the study case report forms. Subjects that demonstrated an increase in NIHSS post ablation should have a formal neurology consult and exam, with appropriate imaging used to corroborate any diagnosis.

[REDACTED]

[REDACTED]

[REDACTED]

[REDACTED]	[REDACTED]
[REDACTED]	[REDACTED]
[REDACTED]	[REDACTED]
[REDACTED]	[REDACTED]
[REDACTED]	[REDACTED]
[REDACTED]	[REDACTED]

[REDACTED]

[REDACTED]

[REDACTED]

[REDACTED]

[REDACTED]

[REDACTED]

[REDACTED]

[REDACTED]

[REDACTED]

[REDACTED]

[REDACTED]

[REDACTED]

[REDACTED]	[REDACTED]
[REDACTED]	[REDACTED]
[REDACTED]	[REDACTED]
[REDACTED]	[REDACTED]

[REDACTED]
 [REDACTED]
 [REDACTED]

5.17.3 Investigator Training

Each investigator will be trained on the use of the Biosense Webster THERMOCOOL SMARTTOUCH® SF Diagnostic/Ablation Deflectable Tip Catheter (“study catheter”). This training will include contact force reference ranges that were used in the pre-clinical (animal), prior clinical (human) studies (EZCF-125, SMART-AF IDE, and SMART-SF IDE clinical trials) and published literature. This will acquaint the investigator with ranges selected by other operators.

5.18 Repeat AF Ablation Procedures

Repeat AF ablations(s) may be performed at the discretion of the physician. Repeat ablations performed during the Medication Adjustment and Therapy Consolidation Periods should utilize the study catheter. The follow-up schedule (Medication Adjustment and Therapy Consolidation periods and exam intervals) will continue based on the initial AF ablation procedure performed, regardless of repeat ablations.

The following assessments should be performed before each procedure utilizing the study catheter:

- Transesophageal Echocardiogram (TEE) – performed within 24 hours prior to the procedure.
- Pregnancy Test – Pre-menopausal women only, performed within 24 hours prior to the procedure.

5.18.1 Repeat Ablation and Primary Effectiveness Classification

- Repeat Ablations in Day 0-180:
 - **Medication Adjustment Period** (Day 0-90): is intended to allow for the patient to receive medication and to allow remodeling to occur. Repeat ablations are discouraged, but subjects requiring a repeat ablation during this period will not be classified as primary effectiveness failures.
 - **Therapy Consolidation Period** (Day 91-180): During this interval, subjects undergoing up to 2 repeat ablations will not be classified as primary effectiveness failures. Circumstances associated with the repeat ablation(s) must be documented in the medical records and recorded in the eCRFs.

During the Medication Adjustment and Therapy Consolidation Periods, a subject may undergo up to 2 repeat ablations. More than 2 repeat ablations during these periods will result in classification as a primary effectiveness failure. Using non-study catheters in repeat ablation procedures during these periods will also be classified as a primary effectiveness failure.

- Repeat Ablation in Day 181-450:
 - During the **Evaluation Period** (Day 181-450), all subjects who have a repeat ablation will be classified as a primary effectiveness failure.
 - The study catheter may NOT be used to perform repeat ablations during the Evaluation Period (Day 181-450)

Table 5-5 illustrates the corresponding primary effectiveness classifications based on the number of repeat ablations in the 3-Month Medication Adjustment Period and 3-Month Therapy Consolidation Period and Evaluation Periods.

Table 5-5 Repeat Ablations and Impact on Primary Effectiveness Classification

Repeat Ablations		
Medication Adjustment Period: (Day 0-90)	Therapy Consolidation Period: (Day 91-180)	Evaluation Period: (Day 181-450)

 ● ≤ 2 repeat ablations are allowed ● Using non-study catheter will be classified as a primary effectiveness failure 		If subject undergoes any repeat ablation; Subject will be classified as a primary effectiveness failure. Use of study catheter not allowed
Repeat Ablations are discouraged Subject will NOT be classified as a primary effectiveness failure.	Subject will NOT be classified as a primary effectiveness failure.	

5.19 Core Laboratory

A core laboratory will be used for objective evaluation of the 24-Hour Holter Monitors, ECGs, and TTMs for the evaluation of recurrence of atrial tachyarrhythmias. Evaluations will be reviewed by a physician. AF episodes will be evaluated per the definition included in this protocol.

6.0 ADVERSE EVENTS

6.1 Adverse Event Recording

An Adverse Event is any untoward medical occurrence, unintended disease or injury, or untoward clinical signs (including abnormal laboratory findings) occurring during a clinical study, whether related to the study device or ablation procedure.

Adverse events will be collected from signing of informed consent throughout study follow-up, at each evaluation and whenever the physician becomes aware of an event. Investigators will determine, at each encounter, whether any adverse events (AE) have occurred, and judge their seriousness and relationship to the study device and procedure.

All adverse events, regardless of classification, seriousness, intensity, outcome, or causality, must be recorded in the electronic CRF(s) in a timely manner throughout the study. Onset date of the event, its treatment, current status (resolved, stabilized, or ongoing), and assessment of its seriousness and relationship to the device should be provided when available. All AEs will be monitored until they are resolved or stabilized (no further changes anticipated).

AF recurrence by itself is considered a recurrence of disease (pre-existing condition), and, therefore, does **not** meet the definition of an AE. Recurrence of pre-existing AFL/AT is also considered recurrence of disease, and not an AE.

The following additional clinical events will not be considered adverse events for this clinical study:

- Minor pericarditis attributable to the ablation procedure defined as pleuritic chest discomfort with or without pericardial rub and ECG changes.
- A trace / trivial / minor pericardial effusion that is asymptomatic, requires no medical intervention, and does not extend hospitalization will not be considered an adverse event.
- AF/AFL/AT recurrence requiring pharmacological or synchronized electrical cardioversion during the hospitalization for the index ablation procedure, or throughout the duration of the study.
- Reablation for AF or pre-existing AFL/AT.

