4.0 STUDY ENDPOINTS

4.1 Primary Endpoints

4.1.1 Primary Effectiveness Endpoint

The primary effectiveness endpoint is defined as the freedom from documented atrial fibrillation, atrial flutter and atrial tachycardia (AF/AFL/AT) (hereinafter collectively referred to as "atrial tachyarrhythmias") recurrence (episodes ≥ 30 secs on Holter recordings/TTM or continuously recorded on the standard 12-leads ECG) during the evaluation period (Day 181-450) and freedom from the following failure modes:

- Acute procedural failure, including:
 - Failure to confirm entrance block in all pulmonary veins post-procedure,
 - Use of a non-study catheter to treat the study arrhythmia for the initial ablation procedure.

Device deficiency of a non-investigational device leading to the use of a non-study catheter (i.e., Stockert 70, SMARTABLATE™ RF Generator and COOLFLOW® Pump, SMARTABLATE™ Irrigation Pump), during the AF procedure will not be considered an acute failure.

- Non-study catheter failure:
 - Use of a non-study catheter to treat the study arrhythmia for repeat ablation procedure during the 3-Month Medication Adjustment or 3-Month Therapy Consolidation Periods.
- Repeat ablation failure, including:
 - > 2 repeat ablation procedures during the 3-Month Medication Adjustment Period / 3-Month Therapy Consolidation Period (Day 0-180) after the index procedure.
 - Any repeat ablation procedure during the Evaluation Period.

Refer to section 5.18 for details.

- AAD failure: Taking a new AAD or a previously failed AAD at a greater than the highest ineffective historical dose for AF during the evaluation period (refer to section 5.14 for details).
- Surgical failure: Undergoing surgical AF ablation or AF surgery any time after the index procedure.

In summary, effectiveness success is defined as freedom from atrial tachyarrhythmia during the Evaluation Period, off or on a previously failed AAD, and not exceeding 2 repeat ablation procedures for an atrial tachyarrhythmia during the 3-Month Medication Adjustment and 3-Month Therapy Consolidation Periods.

This study is designed to compare the primary effectiveness of the investigational device to a pre-determined performance goal of 40%, which is indicated as the minimum acceptable success rate at 12 months for a persistent AF population in the 2012 HRS

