4.2 Secondary Endpoints

4.2.1 Secondary Effectiveness Endpoints

- Acute Procedural Success
 - Acute procedural success is defined as confirmation of entrance block in all PVs.
- 15-Month Single Procedure Success
 - The 15-month single procedure success is defined as freedom from documented AF/AFL/AT recurrence (episodes ≥ 30 secs) during the Evaluation Period after a single ablation procedure. Any repeat ablation procedure during the Evaluation Period will be deemed effectiveness failure for this analysis.
 - The 15-month single procedure success is defined as freedom from documented symptomatic AF/AFL/AT recurrence (episodes ≥ 30 secs) during the Evaluation Period after a single ablation procedure. Any repeat ablation procedure during the Evaluation Period will be deemed effectiveness failure for this analysis.

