6.3 Serious AEs

A serious adverse event (SAE) is any event that meets one or more of the following criteria:

- Lead to a death
- Lead to a serious deterioration in the health of a subject that:
 - Resulted in a life-threatening illness or injury
 - Resulted in a permanent impairment of a body structure or a body function;
 - Required in-patient hospitalization or prolongation of existing hospitalization*
 - Resulted in medical or surgical intervention to prevent permanent impairment to body structure or a body function
- Lead to fetal distress, fetal death or a congenital abnormality or birth defect.

“Hospitalization” means the event necessitated an admission to a health care facility e.g., with at least an overnight stay. Emergency room visits that do not result in admission to the hospital should be evaluated for one of the other serious outcomes.

*Planned hospitalization for a condition present prior to the participant’s enrollment in the study will not meet the definition of an SAE but should nevertheless be included in routine study reporting.

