6.5 Anticipated AEs

An anticipated AE is one that has been reported in previous studies of RF ablation and can be anticipated in this current study as per the risk analysis. Table 6-2 provides a comprehensive list of anticipated AEs.

Table 6-2 Anticipated Adverse Events

Anticipated Adverse Events	
1.	Acute Respiratory Distress Syndrome (ARDS)
2.	Air embolism
3.	Allergic reaction
4.	Anaphylactic shock
5.	Anemia
6.	Allergic reaction to Anesthesia (e.g., hair loss)
7.	Apnea - sedation induced
8.	Arrhythmia: bradycardia
9.	Arrhythmia: tachycardia
10.	Arrhythmia: pro-arrhythmias
11.	Arrhythmia: ventricular tachyarrhythmia / pro-arrhythmia
12.	Aspiration pneumonia
13.	Asthmatic attack
14.	Atelectasis
15.	Atrial fibrillation
16.	Exacerbation of pre-existing arrhythmia
17.	Atrio-Esophageal fistula
18.	Atypical left atrial flutter
19.	AV fistula
20.	Bleeding complications
21.	Bleeding requiring transfusion
22.	Cardiac arrest
23.	Cardiac perforation
24.	Tamponade
25.	Cardiac thrombo-embolism
26.	Cerebro-vascular accident (CVA) / stroke
27.	Chest pain/discomfort
28.	Complete heart block, temporary or permanent
29.	Conduction block: ongoing / resolved
30.	Congestive Heart Failure
31.	Coronary artery dissection
32.	Coronary artery occlusion
33.	Coronary artery spasm
34.	Coronary artery Thrombosis
35.	Death
36.	Deep venous thrombosis
37.	Dislodgement of ICD (Implantable Cardioverter Defibrillator)
38.	Dislodgement of permanent pacing leads
39.	Disseminated Intravascular Coagulation
40.	Dyspnoea
41.	Endocarditis
42.	Epistaxis

Anticipated Adverse Events	
43.	Expressive aphasia
44.	Fainting
45.	Fatigue
46.	Gastro-intestinal NOS
47.	Gastric reflux
48.	Nausea
49.	Gastrointestinal diverticulosis
50.	Heart Failure
51.	Hematoma (local) /ecchymosis
52.	Hemorrhage
53.	Hemothorax
54.	High / increased creatine phosphokinase (CPK)
55.	Hypotension
56.	Hypoxia
57.	Infection, localized
58.	Infection, systemic
59.	Laceration
60.	Leakage of air or blood into the lungs or other organs due to perforation
61.	Liver toxicity
62.	Mobile strands in Inferior Vena Cava
63.	Myocardial Infarction
64.	Neurological disorders (tremor)
65.	Neurological disorders (poor coordination)
66.	Neurological disorders (headache)
67.	Obstruction to the vascular system
68.	Perforation to the vascular system
69.	Damage to the vascular system
70.	Pericardial effusion resulting in tamponade
71.	Pericardial effusion without tamponade
72.	Pericarditis
73.	Peripheral embolus
74.	Peripheral nerve injury

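### Protocol 6.1 exempts cardioverted AFL/AT from adverse events without the pre-existing limit its neighbouring rules carry, so a new post-ablation AFL/AT can be left out of the descriptive SAE endpoints

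*Protocol*

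**What the plan says.** Protocol 6.1 (Adverse Event Recording) treats atrial arrhythmia after ablation in three places.

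- The lead text says that AF recurrence alone is a return of the disease under study and not an AE. It adds: "Recurrence of pre-existing AFL/AT is also considered recurrence of disease, and not an AE".
- A list then opens with "The following additional clinical events will not be considered adverse events for this clinical study". Its third bullet is "AF/AFL/AT recurrence requiring pharmacological or synchronized electrical cardioversion during the hospitalization for the index ablation procedure, or throughout the duration of the study".
- Its fourth bullet is "Reablation for AF or pre-existing AFL/AT".

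Other places bear on how these rules are read.

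- Protocol 4.2.1 defines single-procedure success as "freedom from documented AF/AFL/AT recurrence (episodes ≥ 30 secs) during the Evaluation Period after a single ablation procedure". Protocol 4.1.1 and 4.3 use the same term. None of them requires that the flutter or tachycardia existed before ablation.
- Protocol 6.3 says: "A serious adverse event (SAE) is any event that meets one or more of the following criteria". In-patient admission or a prolonged stay is one of the criteria. Appendix A instead starts its SAE definition from an adverse event.
- Protocol 4.2.2 and SAP 10.5.2.1 define three secondary SAE endpoints (up to 7 days, over 7 to 30 days, over 30 days after the initial ablation). They are reported as percentages of subjects in the Safety Population.
- Protocol 6.13 sends to the GSMC the Primary AEs and the SAEs of cardiac origin within 30 days.

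The SAP has no rule on which post-ablation arrhythmias count as AEs.

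**The concern.** The cardioversion bullet is the only one of the three arrhythmia rules without the pre-existing limit, and it runs for the whole study. Taken at its word, it makes the treatment rather than the event decide whether a new AFL/AT is an adverse event.

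This matters because a new organised atrial arrhythmia may be an effect of the ablation, and admission for cardioversion would meet a seriousness criterion. In a single-arm trial no comparator shares the under-recording, so any error can only lower the device's reported SAE percentages. If sites read the bullet differently, those percentages would also mix two recording rules.

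**Working it through.** No figure in the plan depends on this point, so the check is mainly a comparison of text.

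**Step 1. Apply 6.1 to an AFL/AT first documented after the index ablation.**

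| How it is treated | Rule in 6.1 | Is it an AE? |
|---|---|---|
| No cardioversion or reablation (for example, rate control) | Lead text exempts only pre-existing AFL/AT | Yes, not exempt |
| Reablation | Fourth bullet exempts only AF or pre-existing AFL/AT | Yes, not exempt |
| Cardioversion | Third bullet exempts AF/AFL/AT recurrence, no limit stated | No, if the term means any episode; yes, if it means only the return of an earlier arrhythmia |

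**Step 2. Does the word recurrence supply the missing limit?** Not reliably. In Protocol 4.1.1, 4.2.1 and 4.3 the same term covers any documented AF, AFL or AT, including one first seen after ablation. The list in 6.1 is also introduced as additional to the lead text, which suggests that its bullets go further than the lead text does. And the authors wrote the limit out in the very next bullet.

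**Step 3. Follow the event to the SAE endpoints.** Suppose a new flutter is cardioverted and needs admission or prolongs the index stay. Under Appendix A it must be an AE before it can be an SAE, so an exempted event is not counted. Under 6.3 any event with an admission qualifies, so a site could still report it. Both outcomes are open. On the first path the subject is missing from the window of the SAE endpoints in which the event fell. If the event fell within 30 days, it also misses GSMC submission.

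**Step 4. See where else the event is captured.**

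| Onset | Recurrence-based effectiveness endpoint that counts it |
|---|---|
| Day 0-90 | None |
| Day 91-180 | Only the additional endpoint for Day 91-450 (Protocol 4.3) |
| Day 181-450 | Primary, single-procedure and additional endpoints |

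At any time, Protocol 6.2 requires a hospitalization to be reported to the sponsor, but no text makes such a report an SAE. The gap is widest on Day 0-90, where the event may be in neither a recurrence-based effectiveness endpoint nor a safety endpoint.

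**Step 5. Bound the size.** In one SAE window let N be the Safety Population, k the subjects with an exempted event that would otherwise be an SAE, and s those among the k who have another SAE in the same window. Each endpoint counts subjects, so the s are still counted:

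fall in reported percentage = 100 × (k − s) / N

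This is largest when s = 0. For each 1% of subjects affected, k = 0.01 × N, and the fall is at most 100 × 0.01 × N / N = 1 percentage point, whatever N is. At the enrolment ceiling of 367, 1% is 0.01 × 367 = 3.67 subjects. The Safety Population can be smaller, because enrolled subjects without catheter insertion are left out. The documents give no rate for k or s, so no expected bias can be calculated.

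**The case against.** The strongest reply is that the section can be read consistently. The lead text of 6.1 ties recurrence to a pre-existing condition, and the cardioversion bullet also says recurrence. In ordinary use, a first-ever flutter is not a recurrence. The broader sense comes from effectiveness definitions written for another purpose. This stands as a possible reading, so the section is ambiguous rather than plainly in favour of exempting new AFL/AT. It does not settle the matter, because the protocol itself uses the term in the broader sense and the neighbouring rules found it necessary to state the limit.

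One might cite Table 6-2, which lists "Atypical left atrial flutter" among anticipated AEs, as proof that new flutter must be an AE. That support is weak. The table gathers events reported in earlier ablation studies, and it also lists atrial fibrillation and pericarditis without the limits that 6.1 sets. It cannot show which reading was intended.

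A reader might also infer that these events vanish from the study or from all safety oversight. The documents do not support that. Hospitalizations still reach the sponsor, arrhythmias are collected at discharge and at each follow-up visit (Table 5-1), and documented AFL/AT counts in an effectiveness endpoint from Day 91. For SAEs after 30 days, 6.13 provides no routine GSMC submission in any case. What remains is narrower: possible omission from the three SAE endpoints and, within 30 days, from GSMC submission.

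**Conclusion.** The inconsistency in Protocol 6.1 is real and should be reconciled. A new AFL/AT that is cardioverted with admission or a prolonged stay can be left out of the Early, Peri-Procedural and Late Onset SAE percentages, while the same event managed otherwise would be recorded. The conclusion rests on two readings that the text allows but does not force: recurrence taken as the effectiveness sections use it, and the Appendix A definition of an SAE taken over that in 6.3.

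The direction is known, since any omission lowers the reported percentage. The size is not: it is at most 1 point per 1% of subjects affected in a window, and less where those subjects have another SAE in that window.

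A stronger inference would be that the trial's safety conclusion is biased. The documents do not support it. Atrial arrhythmia is not on the Primary AE list, so the comparison with the 16% performance goal is unchanged. The SAE endpoints are descriptive, with no hypothesis or performance goal (Protocol 7.7, SAP 10.5). Alpha, power, sample size and the success rules do not move.

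**What to change.** Reconcile the third bullet with its neighbours by limiting it to *AF or pre-existing AFL/AT* recurrence requiring cardioversion, leaving the rest of the bullet as it is. Add one sentence: AFL/AT not documented before the index ablation is recorded as an AE and assessed for seriousness, whatever its treatment.

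The cost is one amended bullet, one sentence and a line in the eCRF completion guide. Arrhythmia history is already collected at baseline (Protocol 5.3 and Table 5-1), so new and pre-existing AFL/AT can be told apart without new data. The change concerns recording only and does not affect patient care. The downside is that the reported SAE percentages may be slightly higher.

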6.2 Classification

Any of the following events, and any death or hospitalization while on study, is to be reported to the sponsor immediately. The Sponsor may request additional information after the initial notification.

